#### **D. Description, Risks and Justification of Procedures and Data Collection Tools:**

This project poses minimal risk to all subjects involved. The intervention involves review of decisional support materials and a series of quantitative and qualitative questions. Data collection from participants includes questions and medical record review to screen for eligibility and only limited demographic data will be obtained. There is always a risk that

participants may feel uncomfortable discussing hospice or end-of-life decisions. Participants will be informed of their right to refuse to answer any question they do not wish to answer, and may terminate participation in the study at any point (and that should they decline to participate, answer a question or withdraw this will not affect their medical care).

Data collection and storage has been planned to appropriately protect participant confidentiality. All patients will be given a unique identification number, and study data and identifiable information will always be kept separate. REDCap, the COMIRB-preferred system, will be used to store all survey and enrollment data, and access to both REDCap and the secure server will be limited to study personnel only. All paper documents will be stored in a secure and locked file cabinet in a secure and locked office building – again, all study data paperwork will be stored separate from paperwork with identifiable information (i.e. signed consent forms) and be accessible to study personnel only.

#### **E. Potential Scientific Problems:**

Will participants with low health literacy/numeracy be able to understand decision aid (DA)? A key challenge in DA research is assuring that the resultant products are accessible to all populations. Because most DAs require a minimum level of education, they risk widening disparities by being unavailable to poorer populations. The DA has been developed in accordance with recommendations for clear communication. The current protocol is limited to English speaking and reading participants. In this first stage of intervention assessment we are limited to an English version of the DA since there is currently no staff with credentials to conduct health language translation in Spanish, Amharic, Congolese, Mandarin, Arabic, etc. Upon successful evaluation of this protocol, discussions for DA translation will be conducted.

#### **F. Data Analysis Plan:**

Qualitative Analysis- The open-ended qualitative question will be analyzed using inductive and deductive content analysis. The deductive approach will identify participant knowledge of key domains of hospice. The inductive approach will identify any key misconceptions or fallacies expressed by participants in the study. All qualitative analysis will be done with Atlas.ti. 8.0 (GmbH, Berlin).

Quantitative Analysis- We will compare differences between intervention and control pre/post intervention using t-tests for continuous outcomes and chi-square tests for dichotomous outcomes. We will perform a multivariate analysis of our outcome variables (i.e. hospice knowledge, hospice beliefs and attitudes scale) and look for mediation and/or moderation effects of level medical mistrust, level of perceived discrimination (schedule of racist events) age, race, and gender; while controlling for potential confounders. The total sample size required for phases 1 and 2 is 150participants. The study is powered to achieve an alpha of 0.05 and a medium effect size of 0.5 as determined by a power analysis completed in STATA and confirmed by G\*Power. G\*Power is a specialized program designed for use in social, behavioral and medical research studies.

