### **IV. Research Methods**

#### **A. Outcome Measure(s):**

Overview: The goal of this study is to test whether or not hospice decisional support materials can improve hospice knowledge and attitudes and beliefs towards hospice in older African Americans.

Primary Outcomes: There are three primary outcomes for the study which are change in hospice knowledge measured by the Hospice Knowledge Survey, change in opinions attitudes about hospice care measured by the Hospice Beliefs and Attitudes Scale (HBAS) and decision self-efficacy will be measured the Decision Self-Efficacy Scale. These scales utilize a scoring scheme in which a higher score indicates more knowledge and a more positive view of hospice, and more decision self-efficacy, respectively.

Description of surveys for primary outcomes:

- Knowledge of Hospice Test: The Knowledge of Hospice Test is a 23-item scale with true/false questions. The Cronbach's alpha coefficient for the scale is 0.75 showing good internal reliability.
- Decision Self-efficacy: Is an 11-item instrument that one's self-confidence in decision making. This scale is a validated scale with a Cronbach's alpha of 0.92 and correlates with DCS subscale of being informed ( $r=0.47$ ). Based on our prior study of a decision aid in palliative care, we hypothesize that one of the strongest effects of a decision aid might be to increase self-efficacy of the decision making.
- Hospice Beliefs and Attitude Scale (HBAS): The HBAS is an 8-item scale developed to measure beliefs and attitudes towards hospice care. It has a Cronbach's  $\alpha = .74$  for the scale, indicating a good degree of internal reliability.
- Demographic Form-a brief demographic form to record SES, age, sex and comorbidities such as diabetes, heart disease, and cancer.

Description of qualitative writing sample:

- Hospice knowledge will be qualitatively assessed prior to randomization at the baseline visit to better understand the misconceptions associated with hospice care. Matsuyama et al described a brief qualitative assessment in which participants are asked to describe "what is hospice" in their words. Participants will provide their answers on paper. These brief writings will be analyzed using thematic content analysis.

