**C. Study Design and Research Methods**

Study Design: The study employs a two phase pre-/post-test intervention design or a small pilot randomized control trial (RCT), utilizing a one-to-one randomization scheme. Participants will be randomized into groups after completing the baseline assessments. Pilot RCTs are used to test the acceptance of a new intervention, as well as the feasibility of implementing a new intervention. The proposed study aims to test the efficacy of a paper and video decision aid for hospice care. The intervention group will receive both decision aids and the control group will receive no intervention. All participants will receive the intervention materials at the conclusion of the study regardless of intervention group.

Study Setting: Recruitment will take place at community organizations serving older African Americans and the outpatient primary care clinics for both UCHealth and Denver Health.

Recruitment: The target enrollment is 150 total (75 per arm) participants.

- Community Organizations-will consist of passive recruitment via flyers, listservs, electronic mailing mechanisms and advertisements in newsletters and newspapers.

- **Outpatient Clinics**- potential patients will be identified through weekly chart reviews. The study team will communicate with the outpatient physician by his/her preferred communication method (e.g. email, phone) to determine whether the patients are appropriate to be approached. If eligible and appropriate, a research team member will approach the patient and introduce the study following their clinical encounter. Flyers will also be hung in treatment rooms and common areas of each clinic. Reasons for non-approach will be recorded.
  - **Email/Mailings**-We will also review medical records for potentially eligible patients and send them either an email or letter via US mail describing the study and asking them to contact the study team if they are interested in participating.

**Research Methods:** This will be a 1:1 intervention:control randomization scheme.

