- **Baseline Visit (Aim 1)**- All participants will complete the baseline measurements: brief writing exercise, the Hospice Knowledge Scale, Hospice Beliefs and Attitudes Scale (HBAS), and decision self-efficacy scale (all measurements described above). Additionally, all participants will be asked to briefly describe in writing “what is hospice” in their own words. Prior research shows this brief writing exercise exposes many of the misconceptions of hospice care and provides insights into overcoming knowledge barriers. A trained research assistant will be available to answer questions and provide clarification if necessary. Additionally, the participants’ preferred method of contact or phone number will be recorded for the follow-up visit (Aim2). After completion of baseline surveys, participants will be randomized for Aim 2 of the study.
- **Follow-up Visits (Aim 2)** - Participants randomized to the intervention group will be asked to review the PtDAs within 1 week of the baseline visit. Each participant will be contacted one week after the Phase 1 visit to complete follow-up assessments by phone. All participants, regardless of study arm, will be called 1-month after the baseline visit to complete the follow-up surveys by phone. The control and intervention groups will complete the primary outcomes surveys (Hospice Knowledge, decision self-efficacy & HBAS). The proposed intervention and follow-up are consistent with other shared decision making and PtDA studies.

**Data collection:** For patients who agree to participate, the study coordinator will collect baseline demographic and quantitative data (surveys described above in Section A). The research coordinator will then open the envelope to determine the patient’s allocation. Control patients will be asked to complete the baseline measures at time of enrollment and again at 1-month follow-up. Intervention patients will be given the decision aid and asked to review it within the next week. Then the best way to contact participants for follow-up calls will be recorded. Finally, each participant (control and intervention) will be contacted at one month for the final data point collection. \$25 gift cards will be given for baseline and one-month follow-up surveys.

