- **Baseline visit (control & Intervention)**- All participants will be asked to complete the brief writing exercise, REALM test, Hospice Knowledge Test, Hospice Attitudes and Beliefs Scale, Decision Self-efficacy scale, and demographics.
- **One Week Follow-up call (intervention only)**-Participants will be asked to complete the Hospice Knowledge Test, Hospice Beliefs and Attitudes Scale, Decision Self-efficacy scale, the decision aid acceptability scale and brief decision aid feasibility questionnaire.
- **One Month Follow-up (control & intervention)**-At one month follow-up all participants will be asked to complete the Hospice Knowledge Test, Hospice Beliefs and Attitudes Scale, and the Decision Self-efficacy scale.

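### The plan names only t-tests for comparing the arms on the primary scales; adjusting for the baseline score would tighten the estimates at almost no cost

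*Combined protocol and SAP*

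**What the plan says.** Section IV.F gives one method for comparing the arms on continuous outcomes: "We will compare differences between intervention and control pre/post intervention using t-tests for continuous outcomes and chi-square tests for dichotomous outcomes". It does not say which score enters the t-test.

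Section IV.A partly answers that. It opens with "There are three primary outcomes for the study which are change in hospice knowledge measured by the Hospice Knowledge Survey", and it also words beliefs and attitudes (HBAS) as a change. The third outcome is not worded as a change: "decision self-efficacy will be measured the Decision Self-Efficacy Scale".

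Section IV.C shows what data will exist. Under the baseline visit: "After completion of baseline surveys, participants will be randomized for Aim 2 of the study". At one month, "all participants will be asked to complete the Hospice Knowledge Test, Hospice Beliefs and Attitudes Scale, and the Decision Self-efficacy scale". The one-week call is listed for the intervention arm only, so one month is the only follow-up at which the arms can be compared. On size: "The target enrollment is 150 total (75 per arm) participants".

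Section IV.F also plans a multivariate analysis to look for mediation and moderation. It names knowledge and HBAS as outcomes and adjusts for confounders that it does not list. The baseline score of the outcome is not mentioned.

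**The concern.** A t-test on change subtracts the whole baseline score, which fixes its slope at 1. A t-test on the one-month score ignores baseline, which fixes the slope at 0. A linear model with baseline as a covariate estimates the slope from the data, so in large samples it is at least as precise as either t-test. All the data it needs are already planned.

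Two things are at stake. Section IV.C says that the study tests efficacy, and Section IV.G says that its results are to support a larger multi-site application; both uses are served by the tightest interval that the data allow. Also, the score to be tested for decision self-efficacy is not settled, which leaves a choice open after the data are seen.

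**Working it through.** **Inputs from the documents.** 75 per arm, 1:1; alpha 0.05 (sidedness not stated, taken as two-sided); standardised effect 0.5 (not stated whether in SDs of change or of the raw score).

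**Assumed, because the documents do not give them.** Baseline to one-month correlation rho, from 0.3 to 0.8; ratio k of the one-month SD to the baseline SD, 0.8, 1 or 1.25, with k and rho the same in both arms; completers per arm, 75 or, as an illustration of about 15% loss, 64.

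**The plan's own figure.** For an unadjusted two-sample t-test at effect 0.5, 75 per arm gives 86.0% power (noncentral t). Power of 80% needs 64 per arm (128 in total), and 128/0.85 = 150.6, or 151 with 15% loss. The stated 150 therefore fits a plain t-test with no credit for baseline. It cannot be reproduced uniquely, because neither power nor dropout is stated.

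**Variances, with baseline SD = 1.**
- Change score: 1 + k² − 2·rho·k
- ANCOVA: k²(1 − rho²)
- Ratio of ANCOVA to change at k = 1: (1 − rho²)/[2(1 − rho)] = (1 + rho)/2

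| ANCOVA / change variance | rho 0.3 | 0.5 | 0.7 | 0.8 |
|---|---|---|---|---|
| k = 0.8 | 0.50 | 0.57 | 0.63 | 0.64 |
| k = 1 | 0.65 | 0.75 | 0.85 | 0.90 |
| k = 1.25 | 0.78 | 0.89 | 0.98 | 1.00 |

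In the last cell k·rho = 1, so the true slope is 1 and the change score is already optimal.

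**What this means with equal SDs (k = 1).** The half-width is t(0.975)·SD·√(2/n). The ANCOVA variance is multiplied by 1 + 1/(N − 4) for estimating the slope: 1 + 1/146 = 1.007 at N = 150 and 1 + 1/124 = 1.008 at N = 128. Power is two-sided noncentral t with the same multiplier, on 2n − 2 degrees of freedom (t-test) or 2n − 3 (ANCOVA).

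| k = 1 | rho 0.3 | 0.5 | 0.7 | 0.8 |
|---|---|---|---|---|
| Change-score n per arm equal to ANCOVA on 75 (75/ratio) | 115 | 100 | 88 | 83 |
| ANCOVA n per arm equal to change on 75 (75 × ratio) | 48.8 | 56.2 | 63.8 | 67.5 |
| Half-width, 75 per arm, change / ANCOVA (raw SDs) | 0.382 / 0.309 | 0.323 / 0.280 | 0.250 / 0.231 | 0.204 / 0.194 |
| Half-width, 64 per arm, change / ANCOVA (raw SDs) | 0.414 / 0.335 | 0.350 / 0.304 | 0.271 / 0.251 | 0.221 / 0.211 |
| Power, 75 per arm, 0.5 in SDs of change | 86% / 96% | 86% / 94% | 86% / 91% | 86% / 89% |
| Power, 75 per arm, 0.5 in raw SDs | 73% / 89% | 86% / 94% | 97.5% / 98.9% | 99.8% / 99.9% |

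Leaving the multiplier out of the power calculation would raise the ANCOVA figures by at most 0.3 points.

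**Self-efficacy.** If the t-test were on the one-month score alone, the ratio would be 1 − rho²: 0.91, 0.75, 0.51 and 0.36. This applies only to that scale and only on that reading. With baseline in the model the question disappears: if Y = a + b·arm + c·X, then Y − X = a + b·arm + (c − 1)·X, and the arm effect b is the same.

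**Simulation.** With 20,000 trials per setting, both estimators centred on the true effect of 0.5 (means 0.498 to 0.502). At k = 1 and 75 per arm the variance ratios were 0.651, 0.750, 0.857 and 0.901. In the worst setting (k = 1.25, rho 0.8) they were 1.006 at 75 per arm and 1.008 at 64, which matches the cost of the extra parameter.

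**The case against.** The t-test is valid here, and for two of the three scales the plan already uses baseline by subtraction. The study calls itself a small pilot. Nothing in Sections IV.A or IV.F is wrong on this point, so it is a preference among sound methods. That stands, and it is why the point is graded as optional.

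The multivariate analysis might include the baseline score among its unlisted confounders. It might, but that model looks for mediation and moderation, does not name self-efficacy, and is not presented as the test of the arm difference.

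The size of the gain rests wholly on assumed values. This also stands. With k = 1.25 and rho 0.7 the interval is only 0.6% narrower, and about 74 per arm by ANCOVA matches 75 by change. At rho 0.8 the half-width is 0.243 against 0.242, a trivial loss. If the effect of 0.5 is in raw SDs and rho is 0.7 or more, power with equal SDs is already so high that little is added.

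The self-efficacy question could be settled by one clarifying phrase without a new model. True, though adjustment settles it too. Finally, recovering the precision lost to dropout is not the same as dealing with selective dropout, and ANCOVA on completers does not do the latter.

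**Conclusion.** The point holds as a gain in efficiency; it is neither an error nor a bias. In large samples ANCOVA is never less precise than the t-test on change or on the one-month score, so the conclusion does not depend on how the plan's pre/post wording is read.

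The size is conditional on values that the documents do not give. With equal SDs, the variance saving against change is 35% at rho 0.3, 25% at 0.5, 15% at 0.7 and 10% at 0.8. It is larger if scores are less spread at one month than at baseline, and it shrinks towards nothing if they are more spread and highly correlated. With equal SDs and rho 0.7, 64 completers per arm analysed by ANCOVA carry the precision of 75 analysed by change (1 − 64/75 = 15% loss). That is useful because no dropout allowance is stated, but it is a statement about precision only.

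**What to change.** In Section IV.F, for each of the three primary scales, name as the primary arm comparison a linear model of the one-month score on arm and the baseline score of the same scale, reported as an adjusted mean difference with its 95% confidence interval. Keep the t-test as a sensitivity analysis, and state for each scale whether it uses the change or the one-month score.

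The cost is one sentence and one degree of freedom per model (147 instead of 148 with 150 completers). At worst the variance rises by about 0.7% with 150 completers or 0.8% with 128. No further data, visits or participants are needed.

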## R36 Protocol and Analysis Plan

**Protocol #:** 18-1675

**Project Title:** Underutilization of Hospice in Older African Americans

**Principal Investigator:** [name]

**Mentor:** [name]

**Version Date:** 0124/19

**I. Hypotheses and Specific Aims:** The goal of this study is to determine if poor health literacy and/or insufficient knowledge of hospice care are barriers preventing African Americans from understanding what hospice care is and negatively influences their opinions of hospice care. Additionally, the study will evaluate the influence of perceived discrimination and mistrust in healthcare on hospice knowledge and attitudes and beliefs towards hospice care.

**Aim 1:** To evaluate the relationship between literacy, mistrust and perceived discrimination on hospice knowledge and hospice beliefs and attitudes in older African Americans.

**Aim 2:** To evaluate the effect of hospice decisional support materials on hospice knowledge and attitudes and beliefs about hospice in older African Americans.

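### Three unranked primary outcomes share one alpha of 0.05 with no success or multiplicity rule; if any one positive scale counts as efficacy, familywise error is about 11 to 14%

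*Combined protocol and SAP*

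**What the plan says.** Section IV.A sets the endpoints: "There are three primary outcomes for the study which are change in hospice knowledge measured by the Hospice Knowledge Survey", followed by change on the Hospice Beliefs and Attitudes Scale (HBAS) and decision self-efficacy. None is ranked above the others. Section IV.C repeats the set; at follow-up both arms are to "complete the primary outcomes surveys (Hospice Knowledge, decision self-efficacy & HBAS". The same section states the purpose: "The proposed study aims to test the efficacy of a paper and video decision aid for hospice care".

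Section IV.F is the only analysis section. It compares the arms by t-test for continuous outcomes and gives one significance level and one effect size: "The study is powered to achieve an alpha of 0.05 and a medium effect size of 0.5 as determined by a power analysis". It does not say which outcome was powered, and it gives no success rule, testing order, lead outcome or alpha adjustment. Nor does any other section.

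The lists of outcomes do not match. The sentence in Section IV.F on mediation and moderation reads "We will perform a multivariate analysis of our outcome variables (i.e. hospice knowledge, hospice beliefs and attitudes scale" and leaves out decision self-efficacy. Aim 2 is worded "To evaluate the effect of hospice decisional support materials on hospice knowledge and attitudes and beliefs about hospice in older African Americans", and the overview in Section IV.A asks whether "hospice decisional support materials can improve hospice knowledge and attitudes and beliefs towards hospice in older African Americans". Neither mentions self-efficacy, yet Section IV.A also says "we hypothesize that one of the strongest effects of a decision aid might be to increase self-efficacy of the decision making".

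**The concern.** The plan allows three between-arm tests, each at 0.05, and a claim about efficacy, but does not connect the two. A reader of the results could not tell from the plan whether one positive scale, all three, or a particular one was meant to establish efficacy. Whichever scale reached p<0.05 could then be presented as the efficacy result, and 0.05 would not be the error rate of that claim. Section IV.G says the data are meant to support an application for a multi-site study, so a chance finding on one of three scales could carry weight there.

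The missing rule affects power too. The power of the efficacy claim depends on the rule as much as its error rate does, and neither is defined until a rule is written.

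**Working it through.** **Inputs from the document**
- Alpha 0.05, effect size 0.5, total 150: Section IV.F. 75 per arm: Section IV.C, Recruitment.
- Three primary outcomes: Sections IV.A and IV.C.
- One between-arm time point, one month. The visit list in Section IV.C gives the one-week call to the intervention arm only, so it adds no between-arm test.

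**Assumptions (not stated in the document)**
- Two-sided tests; effect d = 0.5 in SD units of the analysed variable; complete follow-up; equal correlation r between outcomes, from 0 to 0.7.

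**Step 1. The plan's own figure.** Power of a two-sample t-test with n per arm comes from the noncentral t with 2n − 2 degrees of freedom and noncentrality d√(n/2). At n = 75 this is 148 degrees of freedom and 0.5 × √37.5 = 3.06, giving 86.0% at two-sided 0.05. The plan states no power, so 150 cannot be strictly reproduced, and several readings fit:
- a single two-sided test at 0.05 with 75 per arm (86.0%);
- 64 per arm (128) for 80% power, with 15% loss: 128 / 0.85 = 150.6;
- a one-sided Bonferroni test over three outcomes with 75 per arm (81.9%).

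The sample size therefore does not show how alpha was meant to be used.

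**Step 2. Familywise error if any one of three counts.** At r = 0: 1 − (1 − 0.05)³ = 1 − 0.8574 = 14.3%. For r > 0, with c = 1.96, it is 1 − ∫ φ(u) [Φ((c − √r·u)/√(1 − r)) − Φ((−c − √r·u)/√(1 − r))]³ du. Results are in the table. Simulated t-tests at 75 per arm gave 14.4% at r = 0 and 10.7% at r = 0.7.

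**Step 3. The other possible rules.** If all three must be positive at 0.05, the error of the joint claim cannot exceed 5%. Power is then not 86%: at r = 0 with all effects 0.5 it is 0.8604³ = 63.7%, and it rises with positive correlation. If each scale is its own question, each test has 5% error and no joint claim is made.

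**Step 4. Holm's procedure, three outcomes, 75 per arm.** The smallest p-value is tested at 0.05/3 = 0.0167, the next at 0.025, the last at 0.05. Power at 0.0167 is 73.8%, the worst-case first step. Power per outcome with all three effects 0.5 was simulated (200,000 draws).

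| Assumed r | Familywise error, any one of three | Holm power per outcome | Loss from 86.0% (points) |
|---|---|---|---|
| 0 | 14.3% | 82.8% | 3.2 |
| 0.3 | 13.6% | 81.8% | 4.2 |
| 0.5 | 12.5% | 81.3% | 4.7 |
| 0.7 | 10.9% | 80.5% | 5.5 |

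If only one effect is real, Holm power for it is 74.0%, a loss of about 12 points.

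**Step 5. Sensitivity.** With an assumed 15% loss (75 × 0.85 ≈ 64 per arm), a single test has 80.1% power, the first Holm step 65.6%, and Holm per outcome 72.9 to 75.1%. The SD unit also matters. If 0.5 is in SD units of the one-month score but change is analysed, d becomes 0.5/√(2(1 − ρ)), where ρ is the correlation with baseline. First-step power at 75 per arm is then about 57% at ρ = 0.3 and 74% at ρ = 0.5.

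**The case against.** The strongest reply is that the inflation depends on a rule the plan does not contain. Knowledge, attitudes and self-efficacy are separate constructs with separate instruments, and reporting each as its own question is a natural reading that needs no adjustment. This stands as a limit on the claim: a reader might infer that the trial as planned has an 11 to 14% false-positive rate, and the document does not support that. What remains is that the plan does not choose this reading either, and it does state an efficacy aim.

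Second, this is a small pilot. Section IV.C describes such trials as tests of acceptance and feasibility, and Section IV.G speaks of pilot data for a larger study, in which a chance result could be retested. That lowers the stakes but does not fill the gap.

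Third, a reader might infer from the differing lists that the protocol gives rival counts of primary outcomes, three in one place and two in another. It does not. The only explicit count is three, and Section IV.C repeats it. The two-item list in Section IV.F is in the mediation and moderation sentence and refers to outcome variables, while the t-test sentence excludes none. Aim 2 and the overview are short statements of purpose. This is a mismatch of lists to be tidied.

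Fourth, 150 participants might be thought to show either that multiplicity was allowed for or that it was ignored. Step 1 shows that it supports neither.

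**Conclusion.** The concern holds in conditional form. Three unranked primary outcomes, an efficacy aim and a single alpha of 0.05 are stated without any rule connecting them. If one positive scale is taken as efficacy, two-sided familywise error is about 11 to 14%, over an assumed correlation of 0.7 down to 0. It stays at or below 5% if all three are required, and the question does not arise if the scales are reported separately with no joint claim. The omission of decision self-efficacy from the Section IV.F list and from Aim 2 is a secondary inconsistency and does not change the count of three. Given the pilot setting, this is something that should be fixed, but it does not undermine the design.

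**What to change.** Before between-arm results are seen:

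1. State in Section IV.F that the one-month between-arm comparisons of the three primary outcomes are judged by Holm's procedure at familywise two-sided 0.05. Alternatively, state that one named outcome, or a fixed testing order, leads at two-sided 0.05.
2. Reconcile the outcome list in Section IV.F, and Aim 2, with Sections IV.A and IV.C on decision self-efficacy.
3. The plan states no power, so none has to be corrected. If a figure is added, give its assumptions with it: 75 per arm, effect 0.5 in SD units of the analysed variable, two-sided, complete follow-up. It is then about 86% for a single or lead outcome. Under Holm with three outcomes it is about 74% at the first, worst-case step and about 80 to 83% per outcome if all three effects are 0.5.

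The cost is wording only, with no extra participants or data. Holm gives up about 3 to 6 points of power per outcome if all three effects are 0.5, and about 12 points if only one is real. A lead outcome or fixed order keeps 86% for the first outcome, but the others become secondary or conditional on it.
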